## **9.2. Sample Size Considerations**

### **9.2.1. Sample Size Assumptions**

As this study is descriptive in nature and no formal statistical comparisons of PK data will be performed, the sample size of 24 subjects (12 in each cohort) will be recruited such that at least 8 subjects complete the trial. Based on PK parameter CV% of ~50% in subjects with renal impairment or ESRD [refer to GlaxoSmithKline Document Number [RM2008/00267/07](#), 14-Oct-2015.GSK1278863 IB and associated IB supplements for GSK1278863 [GlaxoSmithKline Document Number [2015N266524\\_00](#), 17-Dec-2015; GlaxoSmithKline Document Number [2015N266524\\_01](#), 08-Apr-2016]] for a sample size of at least 8 statistically evaluable subjects, the half width of the 90% confidence interval will be within 56% of the point estimate.

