### **Secondary Comparisons:**

#### **Assessment of Accumulation**

To estimate the extent of accumulation for GSK1278863 and metabolites after repeat dosing, the observed accumulation ratio  $R_0$  will be determined.

$$R_0 = \frac{AUC(0-\tau)_{ss}}{AUC(0-\tau)}$$

where  $AUC(0-\tau)_{ss}$  is AUC from time zero to  $t$  h under steady state and  $AUC(0-\tau)$  is AUC from time zero to *dosing interval* at Day 1.

To evaluate the accumulation ratio, statistical analysis of GSK1278863 and metabolites for both the cohorts combined will be performed after a log transformation of the data.

A mixed effect model will be fitted with day (single and repeat dose), as fixed effects and subject as a random effect. Day 14 will be compared to Day 1 in order to estimate the accumulation ratios,  $R_0 = (AUC(0-\tau, \text{Day14}) : AUC(0-\tau, \text{Day1}))$ . The ratios will be calculated by back-transforming the difference between the LS means.

Using the pooled estimate of variance, 90% confidence intervals will be calculated for  $R_0$ , and back-transformed to the original scale.

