#### **Assessment of Time Invariance**

To evaluate the time invariance ratio, statistical analysis of  $(AUC(0-\infty) \text{ Day 1})$  and  $AUC(0-\tau) \text{ (Day14)}$ , of GSK1278863 and metabolites for both the cohorts combined will be performed after a log transformation of the data.

A mixed effect model will be fitted with day as fixed effects and subject as a random effect. Day 14  $AUC(0-\tau)$  will be compared to Day 1  $AUC(0-\infty)$  in order to estimate the

time invariance ratios,  $R_S = \text{AUC}(0-\tau, \text{Day 14}) : \text{AUC}(0-\infty, \text{Day 1})$ . The ratios will be calculated by back-transforming the difference between the LS means.

**9.3.2.3.2. *Using the pooled estimate of variance, 90% confidence intervals will be calculated for  $R_S$ , and back-transformed to the original scale.* Dialysate PK Parameters**

Peritoneal dialysis excretion amounts and clearance of GSK1278863 and metabolites will be calculated from Day 14 dialysate excretion data (total amount excreted over 24 h) divided by plasma  $\text{AUC}(0-\tau)$ .

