1. INTRODUCTION

The purpose of this reporting and analysis plan (RAP) is to describe the analyses to be included in the Clinical Pharmacology Study Report for Protocol 200942:

Revision Chronology: Protocol		
2013N179529_00	2014-APR-11	Original
2013N179529_01	2014-JUN-06	Amendment No. 1
2013N179529_02	2014-JUN-24	Amendment No. 2
2013N179529_03	2014-JUL-01	Amendment No. 3
2013N179529_04	2014-DEC-12	Amendment No. 4
2013N179529_05	2015-SEP-10	Amendment No. 5
2013N179529_06	2016-JUN-20	Amendment No. 6

All decisions regarding final analysis, as defined in this RAP document, have been made prior to Database Freeze (unblinding) of the study data.

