10.3. Statistical Analyses

Descriptive statistics (n, arithmetic mean and associated 95% confidence interval, standard deviation, minimum, median, maximum) will be calculated for all pharmacokinetic endpoints of GSK1278863 and metabolites by Cohort. In addition geometric means, associated 90% CIs, and estimates of between-subject CVs (CVb (%)), will be calculated for each Cohort where

Geometric mean = $\exp(\text{mean on } \log_e \text{ scale})$

CVb (%) = $\text{SQRT}(\exp(\text{SD}^2) - 1) \times 100$, where SD is the standard deviation of the \log_e -transformed data.

Steady State Assessment

Trough concentration (C_{τ}) samples collected on the specified days (Days 12, 13, 14, and the 24 h post-dose sample on Day 14) will be used to assess attainment of steady state. Individual trough concentration data C_{τ} will be plotted and listed. C_{τ} will be summarized by day and cohort, and the mean and median plots will be provided.

Steady state will be assessed separately for GSK1278863 and metabolites in each cohort.

A linear mixed effects ANOVA model will be used to evaluate steady state for GSK1278863 and each metabolite. The dependent variable will be log-transformed Predose (trough) concentrations (C_{τ}) on Days 12 to 15. Independent variables in the model include day (as a continuous variable) as a fixed effect and subject as a random effect.

Assessment of plasma GSK1278863 and metabolites steady state will be assessed by evaluating the estimated slope for the day parameter and associated 90% CI for both the cohorts combined. A steady state attainment is defined as the 90% confidence interval of the slope including 0.

Secondary Comparisons:

Assessment of Accumulation

To estimate the extent of accumulation for GSK1278863 and metabolites after repeat dosing, the observed accumulation ratio R_0 will be determined.

$$R_0 = \frac{AUC(0-\tau)_{ss}}{AUC(0-\tau)}$$

Where $AUC(0-\tau)_{ss}$ is AUC from time zero to t h under steady state and $AUC(0-\tau)$ is AUC from time zero to dosing interval at Day 1.

To evaluate the accumulation ratio, statistical analysis of GSK1278863 and metabolite PK data for each cohort will be performed separately after a log transformation of the data.

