A mixed effect model will be fitted with day (single and repeat dose), as fixed effects and subject as a random effect. Day 14 will be compared to Day 1 in order to estimate the accumulation ratios, $R_0 = (AUC(0-\tau, \text{Day14}) : AUC(0-\tau, \text{Day1}))$. The ratios will be calculated by back-transforming the difference between the LS means.

Using the pooled estimate of variance, 90% confidence intervals will be calculated for the primary comparisons, and back-transformed to the original scale.

Assessment of Time Invariance

To evaluate the time invariance ratio, statistical analysis of $(AUC(0-\infty) \text{ Day 1})$ and $AUC(0-\tau) \text{ (Day14)}$, of GSK1278863 and metabolites for each cohort will be performed separately after a log transformation of the data.

A mixed effect model will be fitted with day as a fixed effect and subject as a random effect. Day 14 $AUC(0-\tau)$ will be compared to Day 1 $AUC(0-\infty)$ in order to estimate the time invariance ratios, $RS = (AUC(0-\tau, \text{Day 14}) : AUC(0-\infty, \text{Day 1}))$. The ratios will be calculated by back-transforming the difference between the LS means.

Using the pooled estimate of variance, 90% confidence intervals will be calculated for the primary comparisons, and back-transformed to the original scale.

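### SAP 10.3 fits the accumulation and time-invariance models cohort by cohort, whereas the current protocol specifies one estimate from both cohorts combined

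*SAP*

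**What the plan says.** SAP 10.3, on accumulation: "statistical analysis of GSK1278863 and metabolite PK data for each cohort will be performed separately". On time invariance, the analysis is "of GSK1278863 and metabolites for each cohort will be performed separately after a log transformation of the data". Each paragraph ends by saying that "90% confidence intervals will be calculated for the primary comparisons, and back-transformed to the original scale", although both stand under a heading that calls the comparisons secondary.

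Protocol 9.3.2.3.1, on accumulation: "statistical analysis of GSK1278863 and metabolites for both the cohorts combined will be performed after a log transformation of the data". On time invariance, the analysis is "of GSK1278863 and metabolites for both the cohorts combined will be performed after a log transformation of the data". The protocol attaches its 90% intervals to Ro and Rs by name.

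The SAP's Introduction lists the protocol versions up to "Amendment No. 6". In the same section 10.3, the steady-state slope and its 90% interval are for the two cohorts combined.

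**The concern.** The two current texts give different scopes for the same two models, and the SAP does not present the difference as a departure from the protocol. A programmer working from 10.3 would fit one model to CAPD subjects and one to APD subjects and would produce no combined Ro or Rs.

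Both ratios are named secondary endpoints (Protocol 2, SAP 2.1), to be estimated as far as the data allow. In a study this small the scope matters: splitting the subjects widens every interval, and a cohort with one usable subject gets none. The interval label adds to the confusion, since it points to primary comparisons where the protocol means Ro and Rs.

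**Working it through.** **Comparison of the texts**

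| Item | Protocol 9.3.2.3.1 | SAP 10.3 |
|---|---|---|
| Steady-state slope and CI | combined | combined |
| Ro model | combined | each cohort separately |
| Rs model | combined | each cohort separately |
| 90% CI attached to | Ro, Rs | primary comparisons |

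The combined scope is in the SAP's slope paragraph but not in the two ratio paragraphs that follow it.

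**Inputs for the size**

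- Protocol 9.2.1: "Based on PK parameter CV% of ~50% in subjects with renal impairment or ESRD"; at least 8 evaluable subjects; and "the half width of the 90% confidence interval will be within 56% of the point estimate".
- Protocol 1.1.1: 6 completers, 1 CAPD and 5 APD.
- SAP 8: 7 enrolled, 5 completed, no split by cohort.
- Assumptions: complete Day 1/Day 14 pairs and the same within-subject log SD (SDw) in both cohorts. For the percentage figures only, the ~50% is taken as a within-subject CV, which the protocol does not state.

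**Formula.** For n pairs, the 90% half-width of the log ratio is t(0.95, n−1) × SDw × √(2/n), with SDw = √ln(1 + CV²).

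**The protocol's own figure.** At CV 50%, SDw = √ln 1.25 = 0.4724. With n = 8, 1.895 × 0.4724 × √(2/8) = 0.4475, and exp(0.4475) − 1 = +56.4%, against the stated 56%. A single geometric mean with n = 8 gives exp(1.895 × 0.4724/√8) − 1 = +37.2%, which does not match. The stated precision is therefore what a paired ratio from all 8 subjects pooled would give.

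**Loss of precision, independent of CV.** The multipliers t × √(2/n) are:

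| n | 2 | 3 | 4 | 5 | 6 | 7 | 8 |
|---|---|---|---|---|---|---|---|
| multiplier | 6.314 | 2.384 | 1.664 | 1.348 | 1.163 | 1.039 | 0.947 |

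- 1 + 5 (Protocol 1.1.1): APD alone against combined, 1.348/1.163 = 1.16.
- 1 + 4 (assumed split of the SAP's 5 completers): 1.664/1.348 = 1.23.
- At least two pairs in each cohort and at most 7 in all: the smaller cohort's ratio is lowest for 3 + 3, at 2.384/1.163 = 2.05. It is 2.384/1.039 = 2.30 for 3 + 4 and 6.314/1.348 = 4.68 for 2 + 3.
- One pair in a cohort: 2 observations − 2 parameters (intercept, day) = 0 residual degrees of freedom. The ratio can be computed but has no interval at any CV. With 7 analytes and 2 ratios, this would affect up to 14 analyses.

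**Upper 90% half-width as a percentage of the estimate**

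| Pairs | CV 50% | CV 25% (assumed) |
|---|---|---|
| 8 | +56% | – |
| 7 | +63% | – |
| 6 | +73% | +33% |
| 5 | +89% | +39% |
| 4 | +120% | +51% |

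With the planned 8 pairs, CV 50% and both cohorts represented, no cohort's upper half-width reaches 56% under 10.3 as written. The best case is +63% (7 + 1), and a 4 + 4 split gives +120% in each cohort.

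**The case against.** The strongest reply is that the SAP elsewhere reads cohort as CAPD, APD and combined (7.1 and 10.2), and that Table 11.2 summarises the PK parameters by cohort and combined. With complete pairs, the ratio of the combined Day 14 and Day 1 geometric means equals the combined-model point estimate, so mainly the interval would be missing. That much stands. But those conventions govern descriptive summaries, 10.3 drops the gloss and adds that the fits are separate, and SAP Table 1 lists only CAPD and APD. Table 11.2 gives no interval for a ratio.

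The shells do not settle the scope. Exhibits 2 and 3 show one row with no cohort label, and Tables 11.4 and 11.5 carry no cohort note. Nor do the general rules: SAP 7.1 covers deviations from the SAP, not the SAP's own difference from the protocol, and 7.3 provides only for a review if the study stops early.

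Several limits on the size are fair:

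- The documents disagree on completers (6 in Protocol 1.1.1, 5 in SAP 8). If there are five APD completers among at most seven subjects, CAPD has at most two, and the 3 + 3 and 3 + 4 cases cannot occur.
- The 56% comparison concerns the upper side only. The lower half-widths, 1 − exp(−0.4906) = 39% for 7 pairs and 1 − exp(−0.7861) = 54% for 4, are inside 56%. Protocol 9.2.1 also does not tie its figure to Ro or Rs.
- Both endpoints are conditional on what the data permit, which partly covers a missing CAPD interval.
- How the wording arose is only partly clear. The Rs sentence matches superseded protocol text, and the SAP's references cite protocol version _03, but the superseded Ro text did not name cohorts.

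These points limit the illustration, not the conflict of scope.

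**Conclusion.** The concern holds. SAP 10.3 and Protocol 9.3.2.3.1 specify different scopes for Ro and Rs, and nothing else in the SAP restores the combined model estimates and their 90% intervals. This conclusion rests on the current texts alone and needs no assumption about CV or cohort sizes.

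Assuming complete pairs and a common within-subject SD, the APD interval on the log scale is 16% wider than the combined one for the protocol's 1 + 5 completers, and 23% wider for an assumed 1 + 4. The loss of any CAPD interval depends on CAPD supplying only one pair, which the documents make plausible but do not establish. The percentage half-widths depend further on reading the ~50% CV as within-subject.

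The ratios are secondary, no hypothesis is tested, and the primary summaries do not use these models. It should be fixed, but it does not threaten the primary objective.

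**What to change.** In SAP 10.3, give the accumulation and time-invariance paragraphs the protocol's scope, both cohorts combined, in place of separate fits by cohort. In the two interval sentences, replace the reference to primary comparisons with Ro and Rs respectively. Report the number of Day 1/Day 14 pairs by cohort. Treat any per-cohort ratios as supplementary, with an interval only where one can be estimated. It would help to label Tables 11.4 and 11.5 and Exhibits 2 and 3 to match.

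The cost is SAP wording only: two phrases, two interval labels and a count of pairs, plus the optional display labels. No protocol amendment, new data or change in model form is needed.

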11. PHARMACODYNAMIC/BIOMARKER ANALYSES

Plasma erythropoietin and hepcidin concentrations will be presented in graphical and/or tabular form and will be summarized descriptively. The concentration values will be listed by cohort, subject, and time point and will be summarized by cohort and time point.

12. PHARMACOGENETIC ANALYSIS

Samples will be collected and stored. No prospective analyses will be performed.

14. ATTACHMENTS

14.1. Table of Contents for Data Display Specifications

For the Clinical Pharmacology Study Report the following section numbering will apply:

Section 8: Study Population

Section 9: Safety

Section 10: Pharmacokinetic

Section 11: Pharmacodynamic / Biomarker

Section 12: Pharmacogenetics Analysis

Listed below are the planned figures, tables and listings to be produced for inclusion in the 200942 clinical study report:

IDSL standard displays beginning with “CP_” are specific to Clinical Pharmacology and can be found in the IDSL database under “Supporting Documentation -> TST use of IDSL Core Choices -> ClinPharm -> All -> Clin Pharm Options for Statistical Displays”.

14.1.1. Study Population

Table No.	Population	IDSL No. / Example Shell	Title	Additional Programming Notes	Responsibility	Deliverable Priority
9.1	All Subjects	ES1a	Summary of Subject Disposition	By Cohorts and both combined	QSI (Prog)	SAC
9.2	All Subjects	DM1	Summary of Demographic Characteristics	1. By Cohorts and both combined 2.Add BMI, Weight ,Height,	QSI (Prog)	SAC
9.3	All Subjects	DM5	Summary of Race and Racial Combinations	By Cohorts and both combined	QSI (Prog)	SAC
9.4	All Subjects	DM6	Summary of Race and Racial Combinations Details	By Cohorts and both combined	QSI (Prog)	SAC
9.5	Enrolled	NS1	Summary of Number of Subjects by Country and Site ID	By Cohorts and both combined	QSI (Prog)	SAC
9.6	Enrolled	DM11	Summary of Age Ranges	By Cohorts and both combined	QSI (Prog)	SAC

14.1.2. Safety Tables**Tables**

Table No.	Population	IDSL No. / Example Shell	Title	Programming Notes	Responsibility	Deliverable Priority
10.1	All Subjects	CP_AE1p	Summary of All Adverse Events	By Cohorts and both combined	QSI (Prog)	SAC
10.2	All Subjects	CP_AE1p	Summary of Drug-Related Adverse Events	By Cohorts and both combined	QSI (Prog)	SAC
10.3	All Subjects	CP_AE1p	Summary of Serious Adverse Events	By Cohorts and both combined	QSI (Prog)	SAC
10.4	All Subjects	CP_AE1p	Summary of AEs Leading to Permanent Discontinuation of Study Drug or Withdrawal from Study	By Cohorts and both combined	QSI (Prog)	SAC
10.5	All Subjects	AE15	Summary of Common ($\geq 5\%$) Non-serious Adverse Events by System Organ Class and Preferred Term (Number of Subjects and Occurrences)	By Cohorts and both combined	QSI (Prog)	SAC
10.6	All Subjects	AE16	Summary of Serious Adverse Events by System Organ Class and Preferred Term (Number of Subjects and Occurrences)	By Cohorts and both combined	QSI (Prog)	SAC
10.7	All Subjects	LB1	Summary of Haematology Laboratory Values	By Cohorts and both combined	QSI (Prog)	SAC
10.8	All Subjects	LB1	Summary of Change from Baseline in Haematology Laboratory Values	By Cohorts and both combined	QSI (Prog)	SAC
10.9	All Subjects	LB1	Summary of Chemistry Laboratory Values	By Cohorts and both combined	QSI (Prog)	SAC

CONFIDENTIAL

200942

Table No.	Population	IDSL No. / Example Shell	Title	Programming Notes	Responsibility	Deliverable Priority
10.10	All Subjects	LB1	Summary of Change from Baseline in Chemistry Laboratory Values	By Cohorts and both combined	QSI (Prog)	SAC
10.11	All Subjects	EG1	Summary of ECG Findings	By Cohorts and both combined description	QSI (Prog)	SAC
10.11	All Subjects	EG2	Summary of ECG Values	By Cohorts and both combined	QSI (Prog)	SAC
10.12	All Subjects	EG2	Summary of Change from Baseline in ECG Values	By Cohorts and both combined	QSI (Prog)	SAC
10.13	All Subjects	VS1	Summary of Vital Signs	By Cohorts and both combined	QSI (Prog)	SAC
10.14	All Subjects	VS1	Summary of Change from Baseline for Vital Signs	By Cohorts and both combined	QSI (Prog)	SAC

14.1.3. Pharmacokinetic Figures and Tables

Figures

Figure No.	Population	IDSL No. / Example Shell	Title	Programming Notes	Responsibility	Deliverable Priority
11.1	PK	PKCF1p	Individual Plasma GSK1278863 Concentration-Time Plots – by Subjects	1. x-axis should display Actual relative time 2. Include line for LLQ along with footnote defining LLQ value. 3. Include values below LLQ.	QSI (Prog)	SAC
11.2	PK	PKCF1p	Individual Plasma GSK2391220 (M2) Concentration-Time Plots – by Subjects		QSI(Prog)	SAC
11.3	PK	PKCF1p	Individual Plasma GSK2506104 (M3) Concentration-Time Plots – by Subjects		QSI(Prog)	SAC
11.4	PK	PKCF1p	Individual Plasma GSK2487818 (M4) Concentration-Time Plots – by Subjects		QSI(Prog)	SAC
11.5	PK	PKCF1p	Individual Plasma GSK2506102 (M5) Concentration-Time Plots – by Subjects		QSI(Prog)	SAC
11.6	PK	PKCF1p	Individual Plasma GSK2531398 (M6) Concentration-Time Plots – by Subjects		QSI(Prog)	SAC
11.7	PK	PKCF1p	Individual Plasma GSK2531401 (M13) Concentration-Time Plots – by Subjects		QSI(Prog)	SAC

CONFIDENTIAL

200942

Figure No.	Population	IDSL No. / Example Shell	Title	Programming Notes	Responsibility	Deliverable Priority
11.8	PK	PKCF4	Mean (\pm SD) Plasma GSK1278863 Concentration-Time Plots (Linear and Semi-log) by Cohort	1. X-axis displays planned relative time 2. Include line for LLQ along with footnote defining LLQ value. 3. Can do both the cohorts in one page by adding legends	QSI (Prog)	SAC
11.9	PK	PKCF4	Mean (\pm SD) Plasma GSK2391220 (M2) Concentration-Time Plots (Linear and Semi-log) by Cohort	Can do both the cohorts in one page by adding legends	QSI(Prog)	SAC
11.10	PK	PKCF4	Mean (\pm SD) Plasma GSK2506104 (M3) Concentration-Time Plots (Linear and Semi-log) by Cohort		QSI(Prog)	SAC
11.11	PK	PKCF4	Mean (\pm SD) Plasma GSK2487818 (M4) Concentration-Time Plots (Linear and Semi-log) by Cohort		QSI(Prog)	SAC
11.12	PK	PKCF4	Mean (\pm SD) Plasma GSK2506102 (M5) Concentration-Time Plots (Linear and Semi-log) by Cohort		QSI(Prog)	SAC
11.13	PK	PKCF4	Mean (\pm SD) Plasma GSK2531398 (M6) Concentration-Time Plots (Linear and Semi-log) by Cohort		QSI(Prog)	SAC
11.14	PK	PKCF4	Mean (\pm SD) Plasma GSK2531401 (M13) Concentration-Time Plots (Linear and Semi-log) by Cohort		QSI(Prog)	SAC

CONFIDENTIAL

200942

Figure No.	Population	IDSL No. / Example Shell	Title	Programming Notes	Responsibility	Deliverable Priority
11.15	PK	PKCF5	Median (range) Plasma GSK1278863 Concentration-Time Plots (Linear and Semi-log) by Cohort	1. Include bars for range. 2. X-axis displays planned relative time. 3. Include line for LLQ along with footnote defining LLQ value. 3. Can do both the cohorts in one page by adding legends	QSI (Prog)	SAC
11.16	PK	PKCF5	Median (range) Plasma GSK2391220 (M2) Concentration-Time Plots (Linear and Semi-log) by Cohort	Can do both the cohorts in one page by adding legends	QSI(Prog)	SAC
11.17	PK	PKCF5	Median (range) Plasma GSK2506104 (M3) Concentration-Time Plots (Linear and Semi-log) by Cohort		QSI(Prog)	SAC
11.18	PK	PKCF5	Median (range) Plasma GSK2487818 (M4) Concentration-Time Plots (Linear and Semi-log) by Cohort		QSI(Prog)	SAC
11.19	PK	PKCF5	Median (range) Plasma GSK2506102 (M5) Concentration-Time Plots (Linear and Semi-log) by Cohort		QSI(Prog)	SAC
11.20	PK	PKCF5	Median (range) Plasma GSK2531398 (M6) Concentration-Time Plots (Linear and Semi-log) by Cohort		QSI(Prog)	SAC
11.21	PK	PKCF5	Median (range) Plasma GSK2531401 (M13) Concentration-Time Plots (Linear and Semi-log) by Cohort		QSI(Prog)	SAC

CONFIDENTIAL

200942

Figure No.	Population	IDSL No. / Example Shell	Title	Programming Notes	Responsibility	Deliverable Priority
11.22	PK	PKCF1p	Individual Plasma GSK1278863 Concentration-Time Plots – by Cohort	Can do both the cohorts in one page by adding legends	QSI(Prog)	SAC
11.23	PK	PKCF6	Individual Plasma GSK2391220 (M2) Concentration-Time Plots by Cohort (Linear and Semi-Log)	Can do both the cohorts in one page by adding legends	QSI(Prog)	SAC
11.24	PK	PKCF6	Individual Plasma GSK2506104 (M3) Concentration-Time Plots by Cohort (Linear and Semi-Log)		QSI(Prog)	SAC
11.25	PK	PKCF6	Individual Plasma GSK2487818 (M4) Concentration-Time Plots by Cohort (Linear and Semi-Log)		QSI(Prog)	SAC
11.26	PK	PKCF6	Individual Plasma GSK2506102 (M5) Concentration-Time Plots by Cohort (Linear and Semi-Log)		QSI(Prog)	SAC
11.27	PK	PKCF6	Individual Plasma GSK2531398 (M6) Concentration-Time Plots by Cohort (Linear and Semi-Log)		QSI(Prog)	SAC
11.28	PK	PKCF6	Individual Plasma GSK2531401 (M13) Concentration-Time Plots by Cohort (Linear and Semi-Log)		QSI(Prog)	SAC
11.29	PK	PKCF6	Individual Plasma Concentration-Time Plots by Analyte at Predose (Linear and Semi Log)		QSI (Prog)	SAC
11.30	PK	PKCF6	Mean Plasma Concentration-Time Plots by Analyte at Predose (Linear and Semi Log)		QSI (Prog)	SAC
11.31	PK	PKCF6	Median Plasma Concentration-Time Plots by Analyte at Predose (Linear and Semi Log)		QSI (Prog)	SAC

Tables

Table No.	Population	IDSL No. / Example Shell	Title	Programming Notes	Responsibility	Deliverable Priority
11.1	PK	PKCT1	Summary of Plasma GSK1278863 and its metabolites Concentration-Time Data	By Cohort and combined Refer Table 1 for Cohort description	QSI(Prog)	SAC
11.2	PK	PKPT4	Summary of Derived Plasma Pharmacokinetic Parameters of GSK1278863 and its Metabolites	1.By Cohort and combined Refer Table 1 for Cohort description	QSI(Prog)	SAC
11.3	PK	Exhibit 1	Summary of Analysis Results for Steady-State Pharmacokinetic Profile of Trough concentration (C_{τ}) for each Metabolite		QSI(Stat)	SAC
11.4	PK	Exhibit 2	Summary of Results of Statistical Analysis of Derived Plasma GSK1278863 Parameters to Assess Accumulation for each Metabolite		QSI(Stat)	SAC
11.5	PK	Exhibit 3	Summary of Results of Statistical Analysis of Derived Plasma GSK1278863 Parameters to Assess Time Invariance for each Metabolite		QSI(Stat)	SAC
11.6	PK	PKCT1	Summary of Percent Protein Bound of Plasma GSK1278863 and select metabolites		QSI (Stat)	SAC

